8.2.5. Analysis of Safety Data

8.2.5.1. Reactogenicity Data

The presence of each local reaction, each systemic event, fever, use of antipyretic medication at each specific day (day 1, day 2,day 7) will be summarized with number and proportion of subjects reporting such event, for each vaccination. The presence and maximum severity of each local reaction, systemic events, and fever at 'any day 1-7' will be summarized with number and proportion of subjects reporting such event, by each vaccination as well as 'after any vaccination'. The summaries will include 95% Clopper-Pearson's CI.

Proportion differences (Group 1-Group 2), associated 95% CIs and p-values will only be provided, by each vaccination and after any vaccination for the following endpoints:

- any local reactions (overall and by type of event) and any severe local reactions (only overall)
- any systemic events (overall and by type of event) and severe systemic events (only overall)
- any use of anti-pyretics
- any fever and also any temperature above or equal to 39.0-39.9 and 40 degrees centigrade.

Also, the increasing severity and potentiation of local and systemic reactions across all 3 vaccinations will be summarized with number and proportion of subjects with such characteristics, along with 95% exact CI.

The aggregated variable for antipyretic use and fever will also be summarized with number and percentage, along with 95% exact CI (multinomial data),^a for each vaccination.

For local reactions and systemic events, including fever and use of antipyretic medication, the maximum duration of the event will be summarized for each vaccination. The number of unknown durations will also be summarized. The onset day for each local reaction and systemic event will also be summarized.

All of these summaries will be summarized according to the vaccine received. The safety population at each corresponding dose will be used for the analyses for each vaccination. The data summaries will be descriptively presented by group.

^a Goodman's Bonferroni based procedure, with Blyth-Still-Casella intervals as the basis for the Bonferroni procedure (StatXact 9 User Manual)

A listing will be provided for all of the severe reactogenicity data.

8.2.5.1.1. Unscheduled Visits (Unplanned Visits) for Severe Reactions

A listing will be generated for all of the subjects with unscheduled visits (or unplanned visits) for severe reactions.

8.2.5.2. Safety Data Collected Through CRF

8.2.5.2.1. SAE

The percentage of subjects reporting at least one SAE, and the number of episodes will be summarized for each group for each of the first 7 analysis intervals (see [Table 9](#)) with 95% Clopper-Pearson CI for the percentages. Proportion differences (Group 1-Group 2), associated 95% CIs and p-values from Fisher's exact test will be provided for analysis intervals 'During the vaccination phase' and 'Throughout the study'.

Similarly, the percentage of subjects reporting at least one related SAE, total # of related SAEs reported by each group. No between-group proportion differences, associated CIs or p-values for comparisons between groups will be generated for related SAEs.

In addition, for the analysis intervals of vaccination phase, follow-up phase, throughout the study, the SAEs will be summarized by each preferred term (MedDRA) with percentage and number of events for each group. Listings of related SAEs will be provided. All of the SAE will be listed with subject ID, event onset, the most recent vaccination, days of event relative to vaccination, duration of the event, and management and outcome.

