#### 2.2.2. Primary Safety Endpoints

The following endpoints will be applicable in healthy subjects aged  $\geq 24$  months to  $< 4$  years and in healthy subjects aged  $\geq 4$  years to  $< 10$  years at study entry, and in both age strata combined:

- Percentage of subjects reporting local reactions (pain, redness, and swelling) and by severity after each vaccination visit.

- Percentage of subjects reporting systemic events (fever, vomiting, diarrhea, headache, fatigue, muscle pain other than muscle pain at any injection site, and joint pain) and by severity after each vaccination visit.
- Percentage of subjects reporting the use of antipyretic medication after each vaccination visit.
- Percentage of subjects with at least 1 SAE during the following time periods:
  - 30 Days after each vaccination.
  - 30 Days after any vaccination.
  - During the vaccination phase (from the first study vaccination [Visit 1] through 1 month after the last study vaccination [Visit 6]).
  - During the follow-up phase (from 1 month after the last study vaccination [Visit 6] through 6 months after the third study vaccination [Visit 7]).
  - Throughout the study period (from the first study vaccination [Visit 1] through 6 months after the third study vaccination [Visit 7]).
- Percentage of subjects with at least 1 medically attended AE occurring during the following time periods:
  - 30 Days after each vaccination.
  - 30 Days after any vaccination.
  - During the vaccination phase (from the first study vaccination [Visit 1] through 1 month after the last study vaccination [Visit 6]).
  - During the follow-up phase (from 1 month after the last study vaccination [Visit 6] through 6 months after the third study vaccination [Visit 7]).
  - Throughout the study period (from the first study vaccination [Visit 1] through 6 months after the third study vaccination [Visit 7]).
- Percentage of subjects with at least 1 newly diagnosed chronic medical condition occurring during the following time periods:
  - 30 Days after each vaccination.
  - 30 Days after any vaccination.
  - During the vaccination phase (from the first study vaccination [Visit 1] through 1 month after the last study vaccination [Visit 6]).

- During the follow-up phase (from 1 month after the last study vaccination [Visit 6] through 6 months after the third study vaccination [Visit 7]).

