## **9. DATA ANALYSIS/STATISTICAL METHODS**

Detailed methodology for summary and statistical analyses of the data collected in this study will be documented in a statistical analysis plan (SAP), which will be finalized before the start of any analyses and will be maintained by the sponsor. This document may modify the plans outlined in the protocol; however, any major modifications of the primary endpoint definition and/or its analysis will be reflected both in the amended protocol and in the SAP. The SAP amendment will follow the protocol amendment.

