### **9.5. Safety Analysis**

The safety population will be used for all safety analyses. The safety population will include all subjects who have received at least 1 dose of an investigational product and for whom safety information is available. For the safety analysis, subjects will be analyzed according to the investigational product received. Missing safety data will not be replaced or imputed.

The proportion of subjects reporting local reactions at the investigational product administration sites and systemic events within the 7-day period after each vaccination will be descriptively summarized by group. Severities of local reactions and systemic events reported after each vaccination will also be descriptively summarized by group.

Two (2)-sided 95% CIs based on the Clopper-Pearson method will be presented with the proportions.

All of the AEs and SAEs will be categorized according to the Medical Dictionary for Regulatory Activities (MedDRA) and will be summarized. A medically attended AE is defined as a nonserious AE that results in an evaluation at a medical facility. A newly diagnosed chronic medical condition is defined as a disease or medical condition not previously identified that is expected to be persistent or otherwise long-lasting in its effects.

All summaries will show the number and percentage of subjects experiencing at least 1 event and the number of events. Two (2)-sided 95% CIs based on the Clopper-Pearson method will also be presented for the SAE and AE percentages.

Comparisons will be made on the safety endpoints between Group 1 and Group 2. The reactogenicity data and immediate AEs between the vaccine and control will be compared with unconditional exact test. Fisher exact test will be used to compare the endpoints related to AEs, SAE, medically attended AEs, and newly diagnosed medical conditions.

For each subject, the number of days of school missed because of AEs will be aggregated across the vaccination phase. Then summary statistics using mean (standard deviation), median, and range will be descriptively tabulated for the total days by each group.

The CIs and statistical tests presented for the incidence of safety events will not be used to test hypotheses but will be used to determine which events may need further clinical investigation. No adjustment for multiplicity is needed.

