2.1.1. Sample Size and Power

The study sample size is not based on hypothesis-testing criteria. This study will enroll approximately 400 subjects with a randomization ratio of 3:1 (bivalent rLP2086 group : control).

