8.2.5.2.4. Immediate AE

The number and percentage of subjects reporting adverse events during the protocol specified first 30-minute observation period will be summarized by group for each vaccination.

This immediate AE report will be summarized for each vaccination and any vaccination. These summaries will include 95% Clopper-Pearson's CI. Unconditional exact 95% CI on the proportion differences and p-value will also be provided.

The immediate AE categorized as SAE (defined as immediate AE and also meet the definition of SAE) will be summarized similarly.

Immediate AE will not be summarized by preferred term. Instead, these immediate AE will be listed.

8.2.5.2.5. AE

The AEs will be analyzed similar as per [Section 8.2.5.2.1](#), except that only the first 5 intervals from [Table 9](#) are applicable as regular (nonserious, not medically attended) AEs are only collected during the vaccination phase. However, if such AEs during the follow-up phase were recorded in the database, these data will be listed separately.

Note that for the analysis interval of vaccination phase the AEs will be summarized by each preferred term (MedDRA) with percentage and number of events for each group.

Percentages and 95% CIs on the proportion differences will also be provided for adverse events with 1% or above.

In addition, related AEs will also be summarized by each preferred term with percentage and number of events for each group.

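### Unsolicited AEs and medically attended AEs are compared between groups only over the long intervals, not within the 30-day post-vaccination windows where an early excess of common events would show best

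*SAP*

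**What the plan says.** Protocol 2.2.2 lists several periods for the primary safety endpoints on AEs, SAEs, medically attended AEs and newly diagnosed chronic conditions. They include the 30 days after each dose and "30 Days after any vaccination". The primary safety objective (Protocol 2.1.2) is comparative, against the HAV vaccine control.

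Protocol 9.5 commits to comparing the safety endpoints between the groups: "Fisher exact test will be used to compare the endpoints related to AEs, SAE, medically attended AEs, and newly diagnosed medical conditions". It names no interval. SAP 8.1.2.2 repeats the commitment, adds Miettinen-Nurminen CIs for the difference, and also names no interval. Both sections say that the statistics serve to pick out events for further clinical investigation.

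The detailed SAP sections are narrower:

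- **SAEs (SAP 8.2.5.2.1).** Per-group percentages with CIs are given for all seven Table 9 intervals. For the between-group statistics the text reads "exact test will be provided for analysis intervals 'During the vaccination phase' and 'Throughout the study".
- **Medically attended AEs (SAP 8.2.5.2.2) and chronic conditions (SAP 8.2.5.2.3).** The same two intervals are named.
- **AEs (SAP 8.2.5.2.5).** The SAE approach applies, but "only the first 5 intervals from" Table 9. Of the two compared intervals, only the vaccination phase is left.

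The four 30-day intervals (Table 9, rows 1-4) therefore get percentages and CIs for each group and no stated between-group statistic.

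**The concern.** The vaccination phase runs from the first dose to about a month after the third, with long stretches between doses. Background childhood illness in those stretches enters both groups alike. If the vaccine raises the risk of an unsolicited event mainly in the weeks after a dose, a comparison over the whole phase carries the same extra events on a higher background. The proportion with at least one event rises in both arms, and the difference becomes smaller and harder to see.

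The tests are meant as a screen. For common events, the interval chosen for screening is less sensitive than intervals that the plan already defines and tabulates.

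**Working it through.** **Inputs**

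- Group sizes: "This study will enroll approximately 400 subjects with a randomization ratio of 3:1" gives 300 v 100, as in the design table.
- The plan has no safety power or event-rate figure to reproduce: "The study sample size is not based on hypothesis-testing criteria".
- Visit windows (Protocol, Schedule of Activities): Visit 3 at 42-70 days after Visit 1, Visit 5 at 105-126 days after Visit 3, Visit 6 at 28-42 days after Visit 5.
- 30-day interval (SAP Table 9): dose date to dose date + 30, inclusive, so 31 days.
- All event risks below are assumptions.

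**Length of the compared interval**

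- Shortest: 42 + 105 + 28 = 175 days. Longest: 70 + 126 + 42 = 238 days. Working value inside the windows: 56 + 112 + 35 = 203 days.
- Three windows: 3 × 31 = 93 days.
- Share outside the windows: (175 − 93)/175 = 47%; (203 − 93)/203 = 54%; (238 − 93)/238 = 61%.

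This ignores the day or two by which the third window can run past an early Visit 6.

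**Dilution model**

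Let p be the control risk of at least one event in the 93 window days and d the vaccine excess there. Take a constant background hazard h = −ln(1 − p)/93 and no vaccine effect outside the windows. Over a phase of L days, the chance of no background event outside the windows is s = exp(−h(L − 93)). Phase risks are 1 − (1 − p)s and 1 − (1 − p − d)s, so the phase excess is d × s.

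For L = 203:

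- p = 10%: s = 0.9^(110/93) = 0.883.
- p = 40%: s = 0.6^(110/93) = 0.547.

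Fisher power is two-sided at 0.05, by full enumeration, 300 v 100:

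| Windows (vaccine v control) | Phase, 203 days | Excess, windows → phase | Power, windows → phase |
|---|---|---|---|
| 20% v 10% | 29.4% v 20.6% | 10.0 → 8.8 points | 64% → 39% |
| 30% v 20% | 46.2% v 38.6% | 10.0 → 7.7 points | 48% → 27% |
| 50% v 40% | 72.7% v 67.2% | 10.0 → 5.5 points | 40% → 16% |
| 4% v 2% | 6.3% v 4.3% | 2.0 → 2.0 points | 8% → 7% |

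Over 175 to 238 days, phase power runs from 43% to 35% in the first row and from 20% to 14% in the third.

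Medically attended AEs are also compared throughout the study. With 365 days and 20% v 10% in the windows, the risks become 41.2% v 33.9%, a 7.3-point excess, with power 25%.

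**The case against.** **Acute reactions are already compared.** A reader might infer that the plan would miss any acute vaccine effect. It would not. SAP 8.2.5.1 gives differences, CIs and p-values for local reactions, systemic events, fever and antipyretic use on days 1-7, for each dose and any dose. SAP 8.2.5.2.4 does the same for immediate AEs. This stands, and it confines the gap to unsolicited events within 30 days.

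**The 30-day data are reported.** Per-group percentages and CIs are planned, SAEs are listed with their timing relative to vaccination, and the EDMC sees unblinded safety data during the study. A reader could work out a difference from the tables. This stands too. What is missing is the planned difference with its CI and p-value.

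**The SAP may depart from the protocol.** A reader might infer that the SAP breaches Protocol 9.5. The text does not go that far. Protocol 9.5 names no interval, and the vaccination phase and the whole study are also primary endpoint periods, so each event family is compared somewhere. Protocol 9 lets the SAP modify the plan, with the proviso that "any major modifications of the primary endpoint definition and/or its analysis will be reflected both in the amended protocol and in the SAP". Whether leaving some intervals out of descriptive comparisons is a major modification is a matter of judgement. The SAP change log shows that version 2.0 deliberately set out when comparison statistics are given.

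**The restriction is partly inferred.** SAP 8.2.5.1 says outright that its comparisons are limited to a list; SAP 8.2.5.2.1 only names two intervals. Restriction is the likelier reading, but SAP 8.1.2.2 leaves room for the other.

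**The size depends on assumed rates.** The documents give no AE rate, and the loss in the difference runs from almost nothing at 2% control risk to nearly half at 40%. For SAEs and new chronic conditions, if they are as rare as assumed, power is below 10% in either interval, and chronic conditions may be diagnosed after 30 days.

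**Conclusion.** The point holds for AEs and medically attended AEs. The detailed SAP sections compare these events only over long intervals, although the 30-day windows are primary safety endpoint periods and both Protocol 9.5 and SAP 8.1.2.2 describe the comparison without an interval limit. About half of the vaccination phase lies outside the windows. For common events a 10-point excess in the windows would appear as about 5.5 to 8.8 points, with the chance of a Fisher p-value below 0.05 falling by roughly 24 or 25 percentage points (40% to 16%; 64% to 39%).

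These figures rest on assumed control risks of 40% and 10%, a constant background hazard, a vaccine effect confined to the windows, and a 203-day phase. For SAEs and new chronic conditions, if rare, the dilution is negligible.

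The study tests no hypotheses and these statistics are unadjusted, so the issue is sensitivity of screening, with no effect on any formal conclusion. It is an improvement worth considering.

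**What to change.** In SAP 8.2.5.2.2 and 8.2.5.2.5, add Table 9 interval 4 (30 days after any dose) to the intervals that receive the Group 1 − Group 2 difference, Miettinen-Nurminen 95% CI and Fisher p-value, labelled descriptive. Preferably add intervals 1-3 as well: controls receive saline at Month 2, so interval 2 is the one window that sets the vaccine against placebo for unsolicited events. Extending this to SAEs and chronic conditions is optional, and no interval needs to be named as the lead comparison. If the sponsor prefers to keep the present limits, one sentence in SAP 8.1.2.2 should say so and give the reason.

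The cost is SAP wording and extra columns in tables already planned; no new data are needed. The downside is more unadjusted descriptive statistics. Counting one overall comparison per family, interval 4 alone adds 2 families × 3 age sets = 6, and intervals 1-4 add 2 × 4 × 3 = 24.

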8.2.5.2.2. Medically Attended AE

The Medically attended AE will be analyzed as per [Section 8.2.5.2.1](#) in addition there will be:

- An analysis to include the summary of medically attended AE by severity for each analysis interval.
- An analysis to include 'moderate and severe' medically attended AE summary by preferred term for the analysis intervals 5 to 7.
- Proportion differences (Group 1-Group 2), associated 95% CIs and p-values from Fisher's exact test will be provided for analysis intervals 'During the vaccination phase' and 'Throughout the study' for any severe conditions and any severity.

8.2.5.2.3. Newly Diagnosed Chronic Medical Conditions

The percentage of subjects reporting at least one newly diagnosed chronic medical conditions, and the number of episodes will be summarized, by severity and overall, for each group for each of the first 7 analysis intervals (see [Table 9](#)) with 95% Clopper-Pearson CI for the percentages. Proportion differences (Group 1-Group 2), associated 95% CIs and p-values from Fisher's exact test will be provided for analysis intervals 'During the vaccination phase' and 'Throughout the study' for any severity. Similarly, the percentage of subjects reporting

at least one related newly diagnosed chronic medical condition, and total # of related newly diagnosed chronic medical conditions will be reported by each group. No between-group proportion differences, associated CIs or p-values will be generated for related newly diagnosed chronic medical conditions.

In addition, for the analysis intervals of vaccination phase, follow-up phase, throughout the study, the NDCMCs will be summarized by each preferred term (MedDRA) with percentage and number of events for each group.

8.2.5.2.4. Immediate AE

The number and percentage of subjects reporting adverse events during the protocol specified first 30-minute observation period will be summarized by group for each vaccination.

This immediate AE report will be summarized for each vaccination and any vaccination. These summaries will include 95% Clopper-Pearson's CI. Unconditional exact 95% CI on the proportion differences and p-value will also be provided.

The immediate AE categorized as SAE (defined as immediate AE and also meet the definition of SAE) will be summarized similarly.

Immediate AE will not be summarized by preferred term. Instead, these immediate AE will be listed.

8.2.5.2.5. AE

The AEs will be analyzed similar as per [Section 8.2.5.2.1](#), except that only the first 5 intervals from [Table 9](#) are applicable as regular (nonserious, not medically attended) AEs are only collected during the vaccination phase. However, if such AEs during the follow-up phase were recorded in the database, these data will be listed separately.

Note that for the analysis interval of vaccination phase the AEs will be summarized by each preferred term (MedDRA) with percentage and number of events for each group.

Percentages and 95% CIs on the proportion differences will also be provided for adverse events with 1% or above.

In addition, related AEs will also be summarized by each preferred term with percentage and number of events for each group.

8.2.5.2.6. Days Missing School Due to AE's

Descriptive summary statistics will be provided (mean, std, median, and range for numbers of days, number and percentages of subjects) for each group.

8.2.5.2.7. Multiple Events per Subjects (Incidence Rates)

The frequency distribution on number of events reported by each subject will be summarized for each of the following safety variables:

1. Any AE during the vaccination phase.

2. Any SAE throughout the study.
3. Any Medically attended AE throughout the study.
4. Any newly diagnosed chronic medical conditions throughout the study.
5. Any newly diagnosed chronic medical conditions categorized as SAE throughout the study.

For each subject, the number of events reported per year will be estimated by summarizing the total number of events reported over the observation period and standardizing it to an annual rate by multiplying by 365 and dividing by days on study. The overall incidence rate for each of the safety variables will be reported by group.

8.2.5.2.8. Neuroinflammatory and Autoimmune Conditions

A list of preferred terms (MedDRA), to include all of the neuroinflammatory and autoimmune conditions, will be provided by the medical monitor prior to database lock. These events can be SAE, or AE.

A listing of neuroinflammatory and autoimmune conditions matching this preferred terms list will be provided.

8.2.5.3. RRIs Occurring Within 48 hours After Blood Draw

From Visit 7 research-related injuries (RRI) occurring within 48 hours of the blood draw will be collected. A medically important RRI is any untoward medical occurrence that, results in death, is life-threatening (immediate risk of death), requires inpatient hospitalization or prolongation of existing hospitalization, results in persistent or significant disability/incapacity, results in congenital anomaly/birth defect. Medical and scientific judgment is exercised in determining whether an injury is an important medical event. RRIs occurring within 48 hours of a blood draw will be listed in the CSR. Events with an onset equal to the date of Visit 7 will be reviewed by the study lead clinician; unless otherwise documented before the database release, any events with an onset equal to the date of Visit 7 will be included on the appropriate listing(s) of RRIs.

